## 7.11 Subgroup and Other Analyses

Subgroup analyses for primary effectiveness endpoint, clinical success rate, will be performed for sex, target territory (gastrointestinal and non-gastrointestinal), and for etiology (traumatic and non-traumatic). The subgroup analyses will be descriptive in nature and will not be powered for hypothesis testing. Statistical hypothesis testing will be conducted to assess the similarity of the primary effectiveness endpoint across each sub-group using a Fisher's exact test and a significance level of 0.15.

## 7.12 Changes to Planned Analyses

All analyses will be detailed in the Statistical Analysis Plan (SAP). Any changes to the planned analyses will be documented as amendments to the SAP and in the Clinical Study Report.

## 7.13 Interim Analyses

There will be no formal interim analyses in this study. The Data Safety Monitoring Board (DSMB) will review safety data with meetings prespecified in the DSMB Charter and as additionally determined by the Sponsor or the DSMB Chair. The DSMB will review the primary effectiveness

endpoint, since ineffective treatment contributes to the overall benefit-risk profile of subject exposure to the Lava LES.

#### 7.14 Assessment of Poolability

Poolability of data across clinical study sites is justified based on clinical characteristics of the study design; all study sites use the same Protocol; sites are monitored for protocol compliance, and the data gathering instruments are identical. However, a statistical assessment of poolability will be performed by comparing the baseline characteristics across study sites. For categorical baseline variables such as sex, a generalized Fisher's exact test or equivalent test will be used and for quantitative variables, parametric or non-parametric analysis of variance (general linear models or an equivalent procedure) will be used.

The above statistical analyses do not result in an impediment to pooling, but rather assess the balance of baseline covariates across study sites. If any baseline covariate is found to be statistically significant by this process, multivariate analyses will be done to determine if the imbalance affected study outcome. This is done by using both the variable found out of balance and study site as possible covariates.

It may be necessary to combine two or more low enrolling study sites into pseudo-sites to allow these analyses. The justification for pooling all the data to estimate a common effect across study sites requires the homogeneity of response across study sites. A Fisher-Freeman-Halton test analyzing the rates of success for the primary effectiveness endpoint, clinical success rate, will be employed to test whether investigational sites differ with respect to primary effectiveness. The test of inhomogeneity of response will be based on a two-sided test using a 0.15 level of significance. Study sites with fewer than 6 subjects will be excluded for the analysis of poolability.

### 8 ASSESSMENTS AND FOLLOW-UP SCHEDULE

Study participants will be screened for study eligibility pre-procedure and final eligibility will be determined at the time of the diagnostic arteriogram at beginning of the index procedure. Enrollment will occur at the point at which the Investigator makes the decision to perform embolotherapy with the study device (Lava LES) in a previously consented patient. The follow-up period will comprise the post-procedure period through hospital discharge and the 30-day period following the index procedure. Assessments are summarized in the Schedule of Assessments (**Table 7**, below).

**Table 7. Schedule of Assessments**

Assessment	Screening/ Baseline	Index Procedure	Hospital Discharge	30 days ± 7 days*	Unscheduled Visits
------------	---------------------	-----------------	--------------------	-------------------	--------------------

Informed consent	<24 hours before the IP				
Medical history	<24 hours before the IP				
Verification eligibility criteria	<24 hours before the IP	X			
Pregnancy testing	<7 days before the IP				
Physical Examination †	<24 hours before the IP	X	X		X
Diagnostic Angiography		X	X ‡		X ‡
Embolic Therapy with Lava LES		X			
Adverse event assessment		X	X	X	X
Concomitant medications		X	X	X	X
Laboratory testing §	<24 hours before the IP		X		X

IP- Index procedure

\* This assessment can be performed via telephone with a member of the investigational site's research staff or with an in-person visit with the Investigator.

†Physical examination will include vital signs and an examination of the target territory (as appropriate; e.g. the subject's limb) pre-procedure. Physical examination will also include an examination of the access site and target territory at the conclusion of the index procedure and at in-person scheduled or unscheduled follow-up visits. Abnormalities of the vascular system will prompt a duplex ultrasound or another appropriate imaging study to exclude false aneurysm, hematoma, arteriovenous fistula, dissection, or deep venous thrombosis.

‡Diagnostic angiography is repeated after the index procedure for continued bleeding or rebleeding, at the Investigator's discretion. Laboratory

§The following laboratory tests are required to be reported: the lowest hemoglobin reported during the current bleeding episode, the last hemoglobin, platelet count, and international normalized ratio (INR) prior to the index procedure, and the hemoglobin, platelet count and INR at discharge and at any unscheduled visits.

## 8.1 Screening/ Baseline Assessment

Prospective study participants will undergo a baseline, pre-procedure history and physical exam as part of the standard-of-care for these patients. Females deemed by the Investigator to be of reproductive potential must have a negative pregnancy test performed within 7 days of the index procedure. The final disposition (e.g. enrollment, ineligibility, or decision by subject or physician not to enroll) must be noted. Review of the inclusion/ exclusion criteria will be performed to ensure subject meets criteria. If the subject meets all inclusion criteria and does not meet any exclusion criteria, the subject may be invited to participate in the study and informed consent will take place prior to the procedure.

The following procedures will be performed at the Screening visit prior to the procedure. All data must be recorded in the subject's case report form (CRF):

- Demographic information (detailed in **Section 8.1.1**)

- Physical examination with vital signs and directed peripheral vascular examination
- Baseline Characteristics (detailed in **Section 8.1.2**)
- Laboratory assessment (detailed in **Section 8.1.3**)
- Diagnostic angiogram at time of the planned index procedure, performed prior to the point of enrollment in the study; eligibility is, in part, based on the anatomic findings of the angiogram

### **8.1.1 Demographics**

Demographic variables measured at enrollment will include age, sex, race, ethnicity, body weight, height, and calculated basal metabolic index.

### **8.1.2 Baseline Characteristics**

Baseline characteristics will refer to those characteristics present before the index procedure and will include medical comorbidities, selected baseline medications (anticoagulants, antiplatelets), etiology of bleeding (traumatic, iatrogenic, congenital vascular lesion, Mallory-Weiss tear, ulcer, benign neoplasm, malignant neoplasm, unknown, other), location of the target territory (upper gastrointestinal, lower gastrointestinal, non-intestinal visceral, extremity, pulmonary), bleeding vessel(s), duration of bleeding, lowest recorded systolic blood pressure after onset of bleeding, lowest hemoglobin after onset of bleeding, units of red blood cells transfused after onset of bleeding and prior to the index procedure, last platelet count and international normalized ratio prior to the index procedure.

### **8.1.3 Laboratory Assessments**

Clinical laboratory tests are expected to be performed at this visit to establish baseline levels (i.e. hemoglobin, platelet counts, and INR) to evaluate for lowest hemoglobin after onset of bleeding, and the last hemoglobin, platelet count, and INR prior to the index procedure. The panel of tests standardly performed at the institution for patients with similar conditions related to peripheral bleeding will be performed at the Investigator's discretion. It is recognized that specific panels may vary between institutions. Laboratory data will not be specially analyzed but will be used only to support adverse event evaluations.

## **8.2 Treatment Assessment**

Diagnostic angiography will be performed to confirm bleeding prior to the index procedure. The index procedure begins with the start of arterial access and ends when the dressing is applied to the access site. The index procedure is performed under fluoroscopic guidance with administration of contrast as necessary. The Investigator may elect to use provocative methods to identify the site of bleeding and adjunctive embolic agents and devices at their discretion. When utilized, such methods and devices

will be recorded on the procedure electronic case report form (eCRF).j The “treatment phase” begins at the point of administration of Lava.

### 8.3 Target Lesions, Vessels, and Territories

The Target Lesion is specified by the Investigator at the index procedure, after diagnostic angiography but prior to embolization, and is defined as a hemorrhage site planned for embolization with the Lava LES. Up to 4 Target Lesions may be treated in a subject.

Target Vessels are arteries where the tip of the delivery catheter is located at the time Lava administration is planned.k More than one Target Vessel may supply a single Target Lesion. Each Target Lesion is linked to a Target Territory, where the Target Territory is defined as the vascular territory supplied by a Target Vessel, within a single organ, extremity, or tissue bed.l

Non-Target Embolization is defined when Lava is unintentionally administered to a vascular bed outside a Target Territory. Non-target territory is defined as the vascular territory outside of the planned Target Territory specified by the Investigator prior to embolization at that site. Inadvertent embolization of Lava to a Non-Target Territory is an element of the composite MAE endpoint.

### 8.4 Hospital Discharge Assessment

Subjects will be assessed prior to but not more than 48 hours before hospital discharge. A physical examination will be performed. In addition, examination of the access site will be performed, along with an examination of the lower extremity vasculature. Clinical laboratory tests are expected to be performed at this visit to evaluate for lowest hemoglobin after onset of bleeding, last platelet count, and INR. Selected baseline medications (anticoagulants, antiplatelets) will be recorded. Adverse events and any rebleeding episodes or reinterventions will be recorded, as well as units of red blood cells transfused and measures of resource utility such as length of ICU stay and hospital length of stay. An arterial duplex ultrasound examination will be required for abnormalities at the access site (hematoma, mass, diminished peripheral pulses, thrill or bruit) and a venous duplex study will be performed for leg edema or other signs suggestive of deep venous thrombosis or venous injury.

If a subject has not been discharged by the 23rd post-procedure day, the discharge visit may be omitted without protocol deviation; supplanted by the 30-day visit.

j The use of adjunctive embolic devices such as coils or occluders is considered part and parcel of current embolotherapy technique. The use of such devices will not otherwise constitute effectiveness failure of the Lava LES study device. Complications related to the use of adjunctive devices will be considered procedure-related but not device-related events.

k Target Vessels are specified at the time the Investigator is about to begin administration of Lava. Should the catheter be inadvertently displaced during administration, the Target Vessel remains that vessel that the Investigator specified as the planned location of the catheter tip for embolization.

l As an example, for a bleeding duodenal ulcer fed by the gastroduodenal artery and where the Investigator gained access to the gastroduodenal artery, the Target Lesion is the ulcer in the first part of the duodenum, the Target Vessel is the gastroduodenal artery, and the Target Territory is the first part of the duodenum.

## 8.5 Follow-Up Assessment

A 30-day follow-up visit will be performed; with a visit window between 23 and 37 days. The visit may be done via telephone. Any abnormalities will prompt an in-person visit.m Selected baseline medications (anticoagulants, antiplatelets) will be recorded. Adverse events will be recorded, as will any red blood cell transfusions between discharge and the 30 days. An arterial duplex ultrasound examination will be required for abnormalities at the access site (hematoma, mass, diminished peripheral pulses, thrill or bruit) and a venous duplex study will be performed for leg edema or other signs suggestive of deep venous thrombosis or venous injury.

## 8.6 Unscheduled Post Treatment Follow-Up Visits

Unscheduled visits are defined as unplanned visits prompted by recurrent bleeding or a site-reported device- or procedure-related complication. Unrelated visits do not need to be reported as unscheduled visits, but any adverse event, related or unrelated, must be reported on the adverse event eCRF. Subjects who have unscheduled follow-up visits will undergo the same assessments as for the hospital discharge and the unscheduled visit eCRF will contain the same information as the hospital discharge eCRF, with the addition of the reason for the visit.

If an unscheduled visit occurs within the window for the 30-day visit, both the unscheduled visit eCRF and the 30-day visit eCRF must be completed.

When the unscheduled visit is performed for rebleeding, clinical laboratory tests will include the lowest hemoglobin level after discharge, the last hemoglobin level, platelet count, and INR. Selected baseline medications (anticoagulants, antiplatelets) will be recorded. Physical examination and examination of access sites and lower extremity vasculature will be performed. An arterial duplex ultrasound examination will be required for abnormalities at the access site (hematoma, mass, diminished peripheral pulses, thrill or bruit) and a venous duplex study will be performed for leg edema or other signs suggestive of deep venous thrombosis or venous injury. Diagnostic angiography is repeated for continued bleeding or rebleeding at the Investigator's discretion.

## 8.7 Reinterventions

Reinterventions are defined as those secondary procedures, endovascular or open surgical, that occur after the subject has left the angiography suite after the index procedure and are performed as a result of residual bleeding, recurrent bleeding, or a device- or procedure-related events. Procedures unrelated to bleeding or to complications from the device or the procedure are not reported as reinterventions but may be reported as unrelated adverse events (see **Section 10.1**, below).

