## 5.2 Primary Effectiveness Endpoint Definition

The primary effectiveness endpointa is Clinical Success, defined as absence of bleeding from the target lesion after embolization with the Lava LES, without the need for emergency surgery, re-embolization, or other target lesion reinterventions within 30 days of the index procedure. Absence of bleeding is defined as no BARC Type 3 or greater bleeding occurring after the index procedure, either persistent or recurrent. The ascertainment of persistent or recurrent BARC Type 3 or greater bleeding does not include bleeding that occurred prior to the conclusion of the index procedure.

The primary effectiveness endpoint will be adjudicated by the CEC, relying on information from the source documents and/or the core laboratory findings of absence of bleeding.b Effectiveness relates to the target lesion(s) as defined by the Investigator at the index procedure.

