#### **6.4 Peripheral Arterial Hemorrhage**

Subjects will be eligible for enrollment if bleeding is localized within the peripheral arteries, as defined by gastrointestinal hemorrhage (esophagus, stomach, duodenum, small and large intestine), arterial hemorrhage associated with trauma, visceral artery hemorrhage (including splenic, hepatic, adrenal, pancreas, prostate, bladder, and uterus), traumatic musculoskeletal artery hemorrhage, bronchial artery hemorrhage, or iatrogenic arterial hemorrhage.

Patients with hemorrhage from the vessels of the heart, the intracranial vessels, the vertebral or carotid arteries or branches thereof, vessels of the spinal cord, and those with postpartum gynecological hemorrhage will be ineligible for inclusion in the study.

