## 18 DEFINITIONS

Category	Term	Definition
BARC Bleeding	Types 0 – 2 (do not trigger endpoint)	
Type 0: no bleeding
 
Type 1: bleeding that is not actionable and does not cause the patient to seek unscheduled performance of studies, hospitalization, or treatment by a healthcare professional; may include episodes leading to self-discontinuation of medical therapy by the patient without consulting a healthcare professional
 
Type 2: any overt, actionable sign of hemorrhage (eg, more bleeding than would be expected for a clinical circumstance, including bleeding found by imaging alone) that does not fit the criteria for type 3, 4, or 5 but does meet at least one of the following criteria: (1) requiring nonsurgical, medical intervention by a healthcare professional, (2) leading to hospitalization or increased level of care, or (3) prompting evaluation.

	Types 3 – 5 (endpoint trigger)	
Type 3: Clinical, laboratory, and/or imaging evidence of bleeding with specific healthcare provider responses, as listed below:
 
Type 3a:
 
 
• Overt bleeding plus hemoglobin drop of <math>\geq 3</math> to <math><5</math> g/dL* (provided hemoglobin drop is related to bleed)
 
• Overt bleeding plus hemoglobin drop 3 to 5 g/dL, (provided hemoglobin drop is related to bleeding). Hemoglobin drop should be corrected for intracurrent transfusion in which 1 U packed red blood cells or 1 U whole blood would be expected to increase hemoglobin by 1 g/dL.
 
 
Type 3b:
 
 
• Overt bleeding plus hemoglobin drop <math>\geq 5</math> g/dL, provided hemoglobin drop is related to bleed). Hemoglobin drop should be corrected for intracurrent transfusion in which 1 U packed red blood cells or 1 U whole blood would be expected to increase hemoglobin by 1 g/dL.
 
• Cardiac tamponade
 
• Bleeding requiring surgical intervention for control (excluding dental/nasal/skin/hemorrhoid)
 

Category	Term	Definition

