	Catheter breakage	Breakage of the catheter used to deliver Lava, resulting in a luminal catheter defect at the portion of the catheter that resided within the subject's vasculature. Kinks are not considered breakage. Breaks of other catheters, sheaths, and guides do not trigger this component of the composite MAE endpoint.
	Catheter entrapment	Inability to extract the catheter used for Lava delivery, due to adherence to the Lava material, requiring endovascular or open surgical intervention to remove the catheter or retained pieces of the catheter. The endpoint is triggered if pieces of the catheter are retained in the subject's vasculature at the conclusion of the index procedure.
Non-Target Territory		A vascular territory outside of the planned Target Territory specified by the Investigator prior to embolization at that site. Inadvertent embolization of Lava to a Non-Target Territory is an element of the composite MAE endpoint.
Procedure-Related		A procedure-related event is an event that occurs during the index procedure or within 30 days of the index procedure-irrespective of causation but not otherwise classified as a device-related event (i.e. an event that is device-related need not also be reported as procedure-related). As well, procedure-related adverse events include any events related to a remedial procedure necessary to treat the target territory (e.g. a rebleeding episode). An event related to a prior procedure-related event is also considered to be procedure-related.
Reintervention		Defined as those secondary procedures, endovascular or open surgical, that occur after the subject has left the angiography suite after the index procedure and are performed as a result of residual bleeding, recurrent bleeding, or a device- or procedure-related events.
Serious Adverse Event		An adverse event where the outcome is one of the following: 1. Death; 2. Life-threatening, where the patient was at substantial

Category	Term	Definition
		
risk of dying or continued use of the product might have resulted in death;
 
 
3. Hospitalization or prolongation of an existing hospitalization;
 
4. Disability or permanent damage, interfering with the patient's ability to conduct normal life functions;
 
5. Congenital anomaly or birth defect;
 
6. Required intervention to prevent permanent impairment.
 

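### Reintervention covers only endovascular or open surgical procedures, so a target-lesion rebleed below BARC Type 3 that is treated endoscopically, bronchoscopically or cystoscopically most naturally counts as a Clinical Success

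*Protocol*

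**What the plan says.** Protocol 5.2 defines Clinical Success by two conditions. The first concerns bleeding: "Absence of bleeding is defined as no BARC Type 3 or greater bleeding occurring after the index procedure, either persistent or recurrent". The second concerns procedures: "without the need for emergency surgery, re-embolization, or other target lesion reinterventions within 30 days of the index procedure". Protocol 7.3 and SAP section 2 carry the same definition, and the SAP gives no definition of reintervention.

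Reintervention is a defined term. Section 8.7 reads: "Reinterventions are defined as those secondary procedures, endovascular or open surgical, that occur after the subject has left the angiography suite". The Section 18 entry matches it: "Defined as those secondary procedures, endovascular or open surgical, that occur after the subject has left the angiography suite after the index procedure". Both require that the procedure be prompted by residual or recurrent bleeding or by a device- or procedure-related event. Neither names endoscopy, bronchoscopy or cystoscopy.

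Section 18 labels BARC Types 0 to 2 "do not trigger endpoint". Type 2 includes bleeding "requiring nonsurgical, medical intervention by a healthcare professional". Type 3b lists surgical intervention for control and intravenous vasoactive drugs, with no mention of endoscopic hemostasis.

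Two other Section 18 entries differ from 5.2. Clinical Success there has no BARC threshold and refers to reinterventions in the target territory, not on the target lesion. Recurrent Bleeding there includes CEC-adjudicated bleeding on a post-index angiogram as an alternative to BARC Type 3a or greater.

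Section 6.4 admits esophageal, gastric, duodenal, intestinal, bladder and bronchial bleeding. These are sites that an endoscope, cystoscope or bronchoscope can reach.

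**The concern.** The endpoint should show whether the embolized lesion stayed controlled for 30 days. As written, two lesions with the same rebleed can be scored differently because one was re-embolized and the other was treated through an endoscope. The trial has a single arm, so no control group shares the lenient count, and the study passes or fails on this proportion together with the safety proportion.

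The effect has one direction: compared with a count in which every rescue procedure is a failure, the written rule can only leave the observed rate the same or raise it. Any effect would fall mainly on gastrointestinal, bronchial and bladder lesions, and so unevenly across the gastrointestinal versus non-gastrointestinal subgroup of Protocol 7.11. That comparison is descriptive and unpowered, so this is a secondary matter.

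**Working it through.** **Step 1: apply the text to one case.** Take a target lesion that rebleeds on day 5 with a corrected hemoglobin drop of 2 g/dL and no vasoactive drugs. The drop is below the 3 g/dL at which Type 3a starts.

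| Rescue | Text that applies | Result |
|---|---|---|
| Repeat embolization | Re-embolization, 5.2 | Failure |
| Emergency open surgery | Emergency surgery, 5.2; also Type 3b | Failure |
| Urgent laparoscopic surgery | Emergency surgery and Type 3b are not limited to open operations | Probably failure |
| Endoscopic, bronchoscopic or cystoscopic hemostasis, no repeat angiogram | Not named in 5.2, 8.7 or Type 3b; most naturally Type 2 | Success |
| The same, with bleeding shown on a post-index angiogram | 5.2: below the BARC threshold. Section 18, Recurrent Bleeding: qualifies as recurrent | Conflict |

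The fourth row is the gap. The fifth is a contradiction within the Protocol. Repeat angiography is at the Investigator's discretion (Table 7, section 8.6), so the angiographic route will not reach every case.

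**Step 2: reproduce the plan's sample size.** Inputs from Protocol 7.9: performance goal 72%, anticipated rate 84%, one-sided exact test at 0.025, power 80%. With n lesions and X successes, the rule is the smallest r for which P(X ≥ r | n, 0.72) ≤ 0.025. The smallest n giving at least 80% power at 84% is 101, with r = 82, exact alpha 2.27% and power 81.9%. For attrition, 101 / 0.90 = 112.2, rounded up to 113. Both plan figures reproduce.

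The Clopper-Pearson lower limit is the 0.025 quantile of Beta(x, n − x + 1). It is 72.2% at 82/101 (pass) and 71.1% at 81/101 (fail).

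**Step 3: sensitivity of the rule.** Let q be the share of lesions that rebleed below BARC Type 3 and are rescued by an uncounted route. The documents give no value, so q from 1% to 5% (about 1 to 5 of 101 lesions) is an assumption. Lesions are treated as independent, as in the plan's own calculation.

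- Suppose the rate counting all rescues as failures is exactly 72%. The written rule then scores 72% + q, and the chance of passing is P(X ≥ 82 | 101, 0.72 + q).
- Suppose instead that the anticipated 84% already counts such lesions as successes. Counting them as failures gives 84% − q, and power is P(X ≥ 82 | 101, 0.84 − q).

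| q | Chance of passing at 72% + q | Power at 84% − q |
|---|---|---|
| 0% | 2.3% | 81.9% |
| 1% | 3.7% | 73.7% |
| 2% | 5.9% | 64.3% |
| 3% | 9.0% | 54.2% |
| 4% | 13.4% | 44.1% |
| 5% | 19.0% | 34.5% |

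**Step 4: near the anticipated result.** At 85/101 (84.2%), moving 3 lesions to failure leaves 82/101, which passes. Moving 4 leaves 81/101, which fails.

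**The case against.** The strongest reply is that the text does not force a success. Type 3b excludes dental, nasal, skin and hemorrhoid procedures. That list would hardly be needed if only open operations counted, so the CEC could place endoscopic hemostasis in 3b. The CEC adjudicates the endpoint and develops its criteria (Protocol 10.4), and its charter is not in the documents. Some rescued rebleeds will reach Type 3 through the transfusion-corrected hemoglobin drop or vasoactive drugs. Choosing BARC Type 3 as the threshold is open to the sponsor, and the exact test holds its level for the endpoint as written. Nor are the events hidden: rebleeding is a device-related adverse event and prompts an unscheduled visit.

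Much of this stands, and it rules out four stronger conclusions that a reader might draw:

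- That every route other than endovascular or open surgery escapes. Minimally invasive surgical rescue may already fail.
- That nothing else in the Protocol could catch these lesions. The two Section 18 entries could catch some.
- That endoscopic rescue after embolization is shown to be common. The Attachment 1 titles that mention endoscopy mostly describe it failing before embolization.
- That the result is biased upward against the 72% goal. This depends on how the 51 publications in 7.8.2 counted such rescues, which cannot be seen.

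The reply does not remove the gap. CEC criteria must be based on the Protocol, and the Protocol names two routes only. Adverse event reporting does not change the score of the lesion.

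**Conclusion.** The point holds as a defect in the endpoint rule. On the most natural reading of 5.2, 7.3, 8.7, Section 18 and SAP 2, a rebleed below BARC Type 3 controlled by a non-endovascular, non-surgical hemostatic procedure is a Clinical Success, while the same rebleed re-embolized is a failure. Section 18 contradicts 5.2 for rebleeds seen on angiography.

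The size is unknown. The range of 3.7% to 19.0%, against 2.3%, rests on an assumed q of 1% to 5% and on a true all-rescue rate exactly at the goal. It shows how sensitive the 82/101 rule is; it does not estimate the trial's error rate. The planned 101 lesions and 113 subjects are not in question. This should be fixed, with moderate confidence, because the number of lesions affected and the CEC's working criteria cannot be seen.

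**What to change.** In Protocol 8.7 and the Section 18 Reintervention entry, carried to 5.2, 7.3 and SAP 2, state for outcome counting that any secondary hemostatic procedure directed at bleeding from a target lesion after the index procedure, by any route, is a target lesion reintervention and a Clinical Success failure. State that purely diagnostic endoscopy does not count. Align the Section 18 entries for Clinical Success and Recurrent Bleeding with 5.2, covering the BARC threshold, lesion versus territory, and angiographic rebleeding. Record the route of each such procedure on the eCRF if it is not already captured. Make the change before outcomes are known.

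The cost is a few sentences and perhaps one data field. It governs only how outcomes are scored and leaves each site's choice of rescue untouched. The drawback is a possibly slightly lower observed success rate. If the 84% assumption counted such lesions as successes, power would fall as in the last column of the step 3 table, so the sponsor should confirm what that figure assumed.
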